## 6.3. Exploratory Efficacy Endpoints

### 6.3.1. Definition of Exploratory Efficacy Endpoints

PPD

[Redacted content]

PPD

[Redacted]

[Redacted]

[Redacted]

[Redacted]

[Redacted]

[Redacted]

PPD [Redacted]

[Redacted]

**6.4. Other Exploratory Efficacy Endpoint**

PPD [Redacted]

**6.5. Changes from Protocol-Specified Efficacy Analyses**

PPD [Redacted]

[Redacted]

[Redacted]

[Redacted]

## **7. SAFETY ANALYSES**

### **7.1. Adverse Events and Deaths**

#### **7.1.1. Adverse Event Dictionary**

Clinical and laboratory AEs will be coded using the current version of the Medical Dictionary for Regulatory Activities (MedDRA). System organ class (SOC), high level group term (HLGT), high level term (HLT), preferred term (PT), and lower level term (LLT) will be provided in the AE dataset.

#### **7.1.2. Adverse Event Severity**

Adverse events are graded by the investigator as Grade 1, 2, 3, or 4 according to toxicity criteria specified in the protocol. The severity grade of events for which the investigator did not record severity will be categorized as “missing” for tabular summaries and data listings. The missing category will be listed last in summary presentation.

#### **7.1.3. Relationship of Adverse Events to Study Drug**

Related AEs are those for which the investigator selected “Related” on the AE eCRF to the question of “Related to Study Treatment.” Relatedness will always default to the investigator’s choice, not that of the medical monitor. Events for which the investigator did not record relationships to study drug will be considered related to study drug for summary purposes. However, by-subject data listings will show the relationship as missing.

#### **7.1.4. Serious Adverse Events**

Serious adverse events will be identified and captured as SAEs if AEs met the definitions of SAEs that were specified in the study protocol. SAEs captured and stored in the clinical database will be reconciled with the SAE database from the Gilead Drug Safety and Public Health Department before database finalization.

#### **7.1.5. Treatment-Emergent Adverse Events**

##### **7.1.5.1. Definition of Treatment-Emergent Adverse Events**

Treatment-emergent adverse events (TEAEs) are defined as 1 or both of the following:

- Any AEs with an onset date on or after the study drug start date up to the Day 28 visit, or up to 28 days if a subject withdraws early (prior to Day 28) from the study
- Any AEs leading to premature discontinuation of study drug

#### 7.1.5.2. Incomplete Dates

If the onset date of the AE is incomplete and the AE stop date is not prior to the first dosing date of study drug, then the month and year (or year alone if month is not recorded) of onset determine whether an AE is treatment emergent. The event is considered treatment emergent if both of the following 2 criteria are met:

- The AE onset is the same as or after the month and year (or year) of the first dosing date of study drug, and
- The AE onset date is the same as or before the month and year (or year) of the Day 28 visit

An AE with completely missing onset and stop dates, or with the onset date missing and a stop date later than the first dosing date of study drug, will be considered to be treatment emergent. In addition, an AE with the onset date missing and incomplete stop date with the same or later month and year (or year alone if month is not recorded) as the first dosing date of study drug will be considered treatment emergent.

#### 7.1.6. Summaries of Adverse Events and Deaths

Treatment-emergent (TE) AEs will be summarized based on the Safety Analysis Set.

The number and percentage of subjects who experienced at least 1 TEAE will be provided and summarized by SOC and PT, and treatment group. For other AEs described below, summaries will be provided by SOC and PT, and treatment group:

- TEAE by maximum severity
- TEAEs of Grade 3 or higher
- TEAEs of Grade 2 or higher
- All TE treatment-related AEs
- All TE treatment-related AEs by maximum severity
- TE treatment-related AEs of Grade 3 or higher
- TE treatment-related AEs of Grade 2 or higher
- All TE SAEs
- All TE treatment-related SAEs
- All TEAEs leading to premature discontinuation of study drug

- All TEAEs leading to premature discontinuation of study (main study portion)
- All AEs leading to death (ie, outcome of death)

A brief, high-level summary of AEs described above will be provided by treatment group and by the number and percentage of subjects who experienced the above AEs. All deaths observed in the study (with the death date on or after the study drug start date up to Day 28) will be also included in this summary.

Multiple events will be counted only once per subject in each summary. Adverse events will be summarized and listed first in alphabetic order of SOC and HLT within each SOC (if applicable), and then by PT in descending order of total frequency within each SOC. For summaries by severity grade, the most severe grade will be used for those AEs that occurred more than once in an individual subject during the study.

In addition to the above summary tables, all TEAEs, TE treatment-related AEs, and TE SAE will be summarized by PT only, in descending order of total frequency.

In addition, data listings will be provided for the following:

- All AEs, indicating whether the event is treatment emergent
- All AEs of Grade 3 or higher
- All AEs of Grade 2 or higher
- SAEs
- Deaths
- All AEs leading to death (ie, outcome of death)
- AEs leading to premature discontinuation of study drug
- AEs leading to premature discontinuation of study (main study portion)

#### **7.1.7. Additional Analysis of Adverse Events**

Summaries (number and percentage) of subjects who experienced any adverse cardiac events will be provided for each treatment group using the Safety Analysis Set by AE of interest categories and the associated PTs (see [Appendix 3](#)).

#### **7.2. Laboratory Evaluations**

Laboratory data collected during the study will be analyzed and summarized using both quantitative and qualitative methods. Summaries of laboratory data will be provided for the Safety Analysis Set and will include data collected up to Day 28. The analysis will be based on

values reported in conventional units. When values are below the LOQ, they will be listed as such, and the closest imputed value will be used for the purpose of calculating summary statistics as specified in Section 3.7. Hemolyzed test results will not be included in the analysis, but they will be listed in by-subject laboratory listings.

A by-subject listing for laboratory test results will be provided by subject ID number and visit in chronological order for hematology and serum chemistry separately. Values falling outside of the relevant reference range and/or having a severity grade of 1 or higher on the Gilead Grading Scale for Severity of Adverse Events and Laboratory Abnormalities will be flagged in the data listings, as appropriate.

No formal testing will be generated.

### **7.2.1. Summaries of Numeric Laboratory Results**

Descriptive statistics will be provided by treatment group for each laboratory test specified in the study protocol as follows:

- Baseline values
- Values at each postbaseline visit
- Change from baseline at each postbaseline visit

A baseline laboratory value will be defined as the last measurement obtained on or prior to the date/time of first dose of study drug. Change from baseline to a postbaseline visit will be defined as the visit value minus the baseline value. The mean, median, Q1, Q3, minimum, and maximum will be displayed to the reported number of digits; SD values will be displayed to the reported number of digits plus 1.

Median (Q1, Q3) of the observed values for the laboratory tests will be plotted using a line plot by treatment group and visit.

In the case of multiple values in an analysis visit, data will be selected for analysis as described in Section 3.8.3.

### **7.2.2. Graded Laboratory Values**

The Gilead Grading Scale for Severity of Adverse Events and Laboratory Abnormalities will be used to assign toxicity grades (0 to 4) to laboratory results for analysis. Grade 0 includes all values that do not meet the criteria for an abnormality of at least Grade 1. For laboratory tests with criteria for both increased and decreased levels, analyses for each direction (ie, increased, decreased) will be presented separately.

#### 7.2.2.1. Treatment-Emergent Laboratory Abnormalities

Treatment-emergent laboratory abnormalities are defined as values that increase at least 1 toxicity grade from baseline at any postbaseline time point, up to and including Day 28. If the relevant baseline laboratory value is missing, any abnormality of at least Grade 1 observed within the time frame specified above will be considered treatment emergent.

#### 7.2.2.2. Treatment-Emergent Marked Laboratory Abnormalities

Treatment-emergent marked laboratory abnormalities are defined as values that increase from baseline by at least 3 toxicity grades at any postbaseline time point, up to and including Day 28. If the relevant baseline laboratory value is missing, any Grade 3 or 4 values observed within the timeframe specified above will be considered treatment-emergent marked abnormalities.

#### 7.2.2.3. Summaries of Laboratory Abnormalities

Laboratory data that are categorical will be summarized using the number and percentage of subjects in the study with the given response at baseline and each scheduled postbaseline visit.

The following summaries (number and percentage of subjects) for treatment-emergent laboratory abnormalities will be provided by lab test and treatment group; subjects will be categorized according to the most severe postbaseline abnormality grade for a given lab test:

- Graded laboratory abnormalities
- Grade 3 or 4 laboratory abnormalities
- Marked laboratory abnormalities

For all summaries of laboratory abnormalities, the denominator is the number of subjects with non-missing postbaseline values up to and including Day 28.

A by-subject listing of treatment-emergent Grade 3 or 4 laboratory abnormalities and marked laboratory abnormalities will be provided by subject ID number and visit in chronological order. This listing will include all test results that were collected throughout the study for the lab test of interest, with all applicable severity grades displayed.

#### 7.2.3. Liver-related Laboratory Evaluations

Liver-related abnormalities after initial study drug dosing will be examined and summarized using the number and percentage of subjects who were reported to have the following laboratory test values for postbaseline measurements:

- Aspartate aminotransferase (AST): (a) > 3 times of the upper limit of reference range (ULN); (b) > 5 x ULN; (c) > 10 x ULN; (d) > 20 x ULN

- Alanine aminotransferase (ALT): (a) > 3 x ULN; (b) > 5 x ULN; (c) > 10 x ULN; (d) > 20 x ULN
- AST or ALT: (a) > 3 x ULN; (b) > 5 x ULN; (c) > 10 x ULN; (d) > 20 x ULN
- Total bilirubin: (a) > 1 x ULN; (b) > 2 x ULN
- Alkaline phosphatase (ALP) > 1.5 x ULN
- AST or ALT > 3 x ULN and total bilirubin: (a) > 1.5 x ULN; (b) > 2 x ULN
- AST or ALT > 3 x ULN, total bilirubin > 2 x ULN and ALP < 2 x ULN

The summary will include data from all postbaseline visits up to and including Day 28. For individual laboratory tests, subjects will be counted once based on the most severe postbaseline values. For both the composite endpoint of AST or ALT and total bilirubin, subjects will be counted once when the criteria are met at the same postbaseline visit date. The denominator is the number of subjects in the Safety Analysis Set who have nonmissing postbaseline values of all relevant tests at the same postbaseline visit date. A listing of subjects who met at least 1 of the above criteria will be provided.

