Related to allergies:

- 14) Known hypersensitivity or allergy to the IMP, its metabolites, or formulation excipients (microcrystalline cellulose, mannitol, croscarmellose sodium, magnesium stearate, polyvinyl alcohol, titanium dioxide, polyethylene glycol and talc)

15) History of hypersensitivity, anaphylactic reaction, Stevens-Johnson Syndrome, or toxic epidermal necrolysis response to sulfa drugs

Related to laboratory values:

16) Clinically significant kidney dysfunction as defined by:

An estimated glomerular filtration rate (eGFR) < 30 mL/min/1.73 m² as calculated by the Modification of Diet in Renal Disease (MDRD) study 4 parameter equation obtained from screening laboratory measurements or via local laboratory measurements obtained ≤ 7 days prior to Screening. The eGFR may be manually calculated or the reported eGFR value may be used, but any automatically calculated eGFR must be calculated using the MDRD equation.

17) Clinically significant liver function test abnormalities as defined by an ALT or AST > 5 times the ULN obtained in screening laboratory measurements or via local laboratory measurements obtained ≤ 7 days prior to Screening

18) Clinically significant elevations in total bilirubin (TB), as determined by the investigator

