AST (SGOT)	1.25 to 2.50 × ULN	> 2.50 to 5.00 × ULN	> 5.00 to 10.00 × ULN	> 10.00 × ULN
ALT (SGPT)	1.25 to 2.50 × ULN	> 2.50 to 5.00 × ULN	> 5.00 to 10.00 × ULN	> 10.00 × ULN
GGT	1.25 to 2.50 × ULN	> 2.50 to 5.00 × ULN	> 5.00 to 10.00 × ULN	> 10.00 × ULN
Alkaline Phosphatase	1.25 to 2.50 × ULN	> 2.50 to 5.00 × ULN	> 5.00 to 10.00 × ULN	> 10.00 × ULN
Total Amylase	> 1.0 to 1.5 × ULN	> 1.5 to 2.0 × ULN	> 2.0 to 5.0 × ULN	> 5.0 × ULN
Pancreatic Amylase	> 1.0 to 1.5 × ULN	> 1.5 to 2.0 × ULN	> 2.0 to 5.0 × ULN	> 5.0 × ULN
Lipase	> 1.0 to 1.5 × ULN	> 1.5 to 3.0 × ULN	> 3.0 to 5.0 × ULN	> 5.0 × ULN
Albumin Pediatrics <16 years	-	2.0 to < LLN g/dL 20 to < LLN g/L	< 2.0 g/dL < 20 g/L	NA
≥ 16 years	3.0 g/dL to < LLN 30 g/L to < LLN	2.0 to < 3.0 g/dL 20 to < 30 g/L	< 2.0 g/dL < 20 g/L	NA

URINALYSIS				
	Grade 1	Grade 2	Grade 3	Grade 4
Hematuria (Dipstick)	1+	2+	3-4+	NA
Hematuria (Quantitative) See Note below				
Females	>ULN - 10 RBC/HPF	> 10-75 RBC/HPF	> 75 RBC/HPF	NA
Males	6-10 RBC/HPF	> 10-75 RBC/HPF	> 75 RBC/HPF	NA
Proteinuria (Dipstick)	1+	2-3+	4+	NA
Proteinuria, 24 Hour Collection				
Adult and Pediatric ≥ 10 Years	200 to 999 mg/24 h	>999 to 1999 mg/24 h	>1999 to 3500 mg/24 h	> 3500 mg/24 h
Pediatric > 3 Mo to < 10 Years	201 to 499 mg/m ² /24 h	>499 to 799 mg/m ² /24 h	>799 to 1000 mg/m ² /24 h	> 1000 mg/ m ² /24 h
Glycosuria (Dipstick)	1+	2-3+	4+	NA

Notes:

- Toxicity grades for Quantitative and Dipstick Hematuria will be assigned by Covance Laboratory, however for other laboratories, toxicity grades will only be assigned to Dipstick Hematuria.
- With the exception of lipid tests, any graded laboratory test with a result that is between the LLN and ULN should be assigned Grade 0.
- If the severity of a clinical AE could fall under either one of two grades (eg, the severity of an AE could be either Grade 2 or Grade 3), select the higher of the two grades for the AE.

CARDIOVASCULAR				
	Grade 1	Grade 2	Grade 3	Grade 4
Cardiac Arrhythmia (general) (By ECG or physical exam)	Asymptomatic AND No intervention indicated	Asymptomatic AND Non-urgent medical intervention indicated	Symptomatic, non-life-threatening AND Non-urgent medical intervention indicated	Life-threatening arrhythmia OR Urgent intervention indicated
Cardiac-ischemia/Infarction	NA	NA	Symptomatic ischemia (stable angina) OR Testing consistent with ischemia	Unstable angina OR Acute myocardial infarction

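### The liver table ignores baseline, and the treatment-emergent graded table only partly makes up for it, so new crossings of the liver cut-offs per arm are not reported

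*SAP*

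**What the plan says.** SAP 7.2.3 (Table 15.11.6.5) sets the rule: "Liver-related abnormalities after initial study drug dosing will be examined and summarized using the number and percentage of subjects", namely those "who were reported to have the following laboratory test values for postbaseline measurements", up to and including Day 28. The rows include "AST or ALT: (a) > 3 x ULN; (b) > 5 x ULN; (c) > 10 x ULN; (d) > 20 x ULN" (with the same four cut-offs for AST and for ALT separately), "Total bilirubin: (a) > 1 x ULN; (b) > 2 x ULN", ALP above 1.5 x ULN, and three composites: AST or ALT above 3 x ULN with bilirubin above 1.5 x ULN, the same with bilirubin above 2 x ULN, and the latter with ALP below 2 x ULN. "For individual laboratory tests, subjects will be counted once based on the most severe postbaseline values". No row has a baseline condition, a shift or a treatment-emergent flag. A listing of subjects meeting any criterion is planned.

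Protocol 4.3 (criterion 17) excludes "Clinically significant liver function test abnormalities as defined by an ALT or AST > 5 times the ULN". Criterion 18 leaves bilirubin to the investigator's judgement of clinical significance. No criterion mentions ALP.

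A separate graded table uses baseline. SAP 7.2.2.1 defines treatment-emergent abnormalities as "values that increase at least 1 toxicity grade from baseline at any postbaseline time point", up to Day 28, and SAP 7.2.2.3 reports them by single test and worst post-baseline grade. In Protocol Appendix 5, Grade 2 for AST and ALT is "> 2.50 to 5.00 × ULN".

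**The concern.** The table is framed as describing abnormalities after the first dose, but its counts mix two kinds of subject: those who crossed a cut-off on study and those who entered above it and stayed there. A subject who enters with ALT at 4 x ULN and improves to 3.5 x ULN counts in the > 3 x ULN row.

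In a trial of about 60 subjects randomized 2:1, one or two such subjects can change how a row looks in either direction. Liver findings have some prior interest here. In the Phase 2a challenge study (Protocol 1.2.4.7), raised ALT was more common on presatovir (14.9% against 9.4%), although raised AST was less common (5.7% against 15.1%). The useful safety quantity is the number of new crossings per arm, so the question is whether any planned summary gives it.

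**Working it through.** The plan states no figure on this point to reproduce. The check applies the protocol's own grade bands and the one-grade rule to each cut-off.

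**Inputs.** Cut-offs: SAP 7.2.3. Entry limits: Protocol 4.3. Grade bands: Protocol Appendix 5 (AST, ALT and ALP: Grade 1 1.25 to 2.5, Grade 2 > 2.5 to 5, Grade 3 > 5 to 10, Grade 4 > 10 x ULN; bilirubin: Grade 1 > 1 to 1.5, Grade 2 > 1.5 to 2.5, Grade 3 > 2.5 to 5, Grade 4 > 5 x ULN). Treatment-emergent rule: SAP 7.2.2.1. Size: 60 subjects at 2:1, so 60 x 2/3 = 40 and 60 x 1/3 = 20.

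**Step 1: rows a subject can already meet at entry.** There are 4 + 4 + 4 rows for AST, ALT and either, 2 for bilirubin, 1 for ALP and 3 composites, 18 in all. The > 5, > 10 and > 20 x ULN rows (3 x 3 = 9) lie above the entry limit. That leaves 9: three > 3 x ULN rows, two bilirubin rows, one ALP row and three composites.

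**Step 2: where each cut-off falls on the grading scale.**

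| Cut-off (x ULN) | Grade just above | Cut-off is a grade boundary? | Baselines from which a new crossing that stays in that grade is not treatment-emergent |
|---|---|---|---|
| AST/ALT 3 | 2 | No | > 2.5 to 3 |
| Bilirubin 1 | 1 | Yes | None |
| Bilirubin 2 | 2 | No | > 1.5 to 2 |
| ALP 1.5 | 1 | No | 1.25 to 1.5 |
| Composites | Not graded | – | No counterpart |

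**Step 3: worked pairs for AST/ALT > 3 x ULN.**

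| Baseline to worst value | Grades | Liver table > 3 | Treatment-emergent | New crossing |
|---|---|---|---|---|
| 4.0 to 4.0 | 2 to 2 | Yes | No | No |
| 4.0 to 6.0 | 2 to 3 | Yes | Yes | No |
| 1.0 to 4.0 | 0 to 2 | Yes | Yes | Yes |
| 2.6 to 4.9 | 2 to 2 | Yes | No | Yes |
| 1.0 to 2.8 | 0 to 2 | No | Yes | No |

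The graded table correctly drops the first pair and keeps the third. It cannot tell the fourth from the first, and it flags the second and fifth although neither is a new crossing of 3 x ULN.

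**Step 4: can the two tables be combined?** Take two pairs of subjects. Pair A: 4.0 to 4.0, and 1.0 to 2.8. Pair B: 1.0 to 4.0, and 1.0 to 1.0. Each gives one subject in the liver table's > 3 row and one treatment-emergent Grade 2. Pair A has no new crossing and pair B has one. The number of new crossings is therefore not determined by the two tables together.

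**Step 5: size.** One subject moves a row by 1/40 = 2.5 points or 1/20 = 5 points. The documents give no share of subjects entering above a cut-off, so this share is assumed. With share p, the chance of at least one such subject on presatovir and none on placebo is [1 − (1 − p)^40] x (1 − p)^20.

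| Assumed p | Expected, presatovir / placebo | Chance |
|---|---|---|
| 1% | 0.4 / 0.2 | 27% |
| 3% | 1.2 / 0.6 | 38% |
| 5% | 2 / 1 | 31% |
| 10% | 4 / 2 | 12% |

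As illustration only: if 3 of 60 enter above a cut-off and stay there, all three fall on presatovir with probability C(40,3)/C(60,3) = 9880/34220 = 0.29 (shown as 7.5% against 0%), and all three on placebo with probability 1140/34220 = 0.03.

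**The case against.** The best reply is that the two tables do different jobs. Table 15.11.6.5 reports absolute thresholds and says that its values are post-baseline; the treatment-emergent tables report change from baseline. Baseline values and changes are summarized by arm (SAP 7.2.1), all laboratory results are listed by subject in time order (SAP 7.2), and every subject in the liver table is listed. With a handful of cases, a reader can look up each baseline. The same rule applies to a randomized placebo arm, and no formal testing is planned. A 3-to-0 split with probability 0.29 is unremarkable in itself.

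Much of this stands: it limits the risk of misreading and makes the point minor. It does not supply the missing count. Change-from-baseline summaries describe distributions rather than crossings, listings give no count per arm, and nothing says that baseline elevation will be flagged. The SAP uses baseline where it matters elsewhere: new abnormalities and a shift table for ECG (7.5), and a shift table for troponin (7.6).

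A reader might infer that the graded table cannot separate pre-existing from new elevations at all. The documents do not support that: it excludes an unchanged elevation such as 4.0 to 4.0 and includes a rise from 1.0 to 4.0. Its failure is confined to cut-offs inside a grade, the composites, and the absence of baseline grade from its layout.

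**Conclusion.** The point holds as a limited reporting gap. SAP 7.2.3 sets no baseline condition, entry above the AST/ALT 3 x ULN, bilirubin and ALP cut-offs is permitted, and the graded table closes the gap only in part. New crossings per arm cannot be recovered from the planned summaries for the rows concerned. At the bilirubin 1 x ULN cut-off the graded table misses no new crossing, but it also includes subjects who entered in Grade 1 and rose to Grade 2.

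Nine of 18 rows are affected. The > 5, > 10 and > 20 x ULN rows are essentially unaffected because entry above 5 x ULN is excluded. Each pre-existing case is worth 2.5 or 5 points, assuming that all 40 and 20 subjects are evaluable. How many will occur is unknown; the shares above and the 3-of-60 example are assumptions.

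A reader might go further and infer that a conclusion on liver injury would rest on the Hy's Law-type rows. The documents do not support this. To meet the bilirubin > 2 x ULN composite at entry, a subject would need AST or ALT above 3 x ULN together with a bilirubin above 2 x ULN that the investigator judged not clinically significant. The protocol's Hy's Law criteria (3.5) also require clinical verification that the effect is not due to disease or another cause.

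No primary analysis, power or alpha is affected.

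**What to change.** Add to SAP 7.2.3 that, alongside the current counts, Table 15.11.6.5 will give the number and percentage among subjects at or below the cut-off at baseline (applied to numerator and denominator) for the AST, ALT and AST-or-ALT > 3 x ULN rows, both bilirubin rows and the ALP row. For the three composite rows, use subjects who did not meet that composite at baseline; a subject with one raised component at entry then still counts if the full composite first appears on study.

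Treat a missing baseline as not elevated, in line with SAP 7.2.2.1. Flag subjects elevated at baseline in Listing 16.2.8.1.6.

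The cost is a short addition to the SAP text, an extra pair of columns for nine rows and one flag in a listing. Baseline values are already collected. The drawback is smaller denominators in a descriptive table.

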3.5. Discontinuation Criteria

Reasons for potential premature discontinuation from IMP dosing include:

- Any Grade 3 or 4 AE or SAE
- Intercurrent illness that would, in the judgment of the investigator, affect the subject's ability to receive IMP (eg, unable to ingest oral dose)
- ALT or AST > 5× ULN
- Worsening of clinical symptoms with no other acceptable explanation
- Hy's Law criteria are met:
 - Evidence of injury: elevation of the ALT or AST by > 3× ULN
 - Evidence of dysfunction: elevation of the total bilirubin (TB) by > 2× ULN without an elevation of the alkaline phosphatase (ALP) by > 2× ULN
 - Clinical verification to ensure effect is health product-induced and not induced by disease or another cause of injury

In the event that any of the above criteria are met, the Principal Investigator (PI) will review the case in detail and discuss with the Gilead Medical Monitor whether the subject should be discontinued from IMP. If close monitoring of ALT, AST, ALP, and TB per Section 6.7.6 is not possible, IMP will be discontinued.

Reasons for premature discontinuation from the study include:

- Subject request to discontinue for any reason
- Subject noncompliance
- Pregnancy during the study; refer to Section 7.7.2
- Discontinuation of the study at the request of Gilead, a regulatory agency or an institutional review board or independent ethics committee (IRB/IEC)

If a subject prematurely discontinues from IMP dosing, he/she will remain on study and will continue with all subsequent study Day visits and assessments, with the exception of IMP administration.

If a subject prematurely discontinues from the study, every attempt should be made to bring the subject back for the Early Termination procedures. See Section 6.5.2 for more information.

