Any test showing an increase of serum AST or ALT $> 3 \times$ ULN or TB $> 2 \times$ ULN, will be repeated within 48 to 72 hours for ALT, AST, ALP, and TB. If the repeat values are unchanged or are normalizing, monitoring will continue at weekly intervals until the results are acceptable or normalized. If any value has increased further from normal, immediate close observation is required. If close monitoring is not possible, IMP administration will be discontinued.

Local urine or serum pregnancy tests will occur for all females of childbearing potential at Screening, within 1 day prior to IMP administration, and on Days 7 and 14.

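### SAP 7.2.3 counts the transaminase-plus-bilirubin composites only on a single visit date, so a bilirubin rise that follows the transaminase fall is left out of the composite rows

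*SAP*

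**What the plan says.** Protocol 3.5 lists Hy's Law among the reasons for possible discontinuation of study drug. It has three elements:

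- Injury: "Evidence of injury: elevation of the ALT or AST by > 3× ULN".
- Dysfunction: "elevation of the total bilirubin (TB) by > 2× ULN without an elevation of the alkaline phosphatase (ALP) by > 2× ULN".
- Causality: "Clinical verification to ensure effect is health product-induced and not induced by disease or another cause of injury".

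None of the three says when the elevations must occur relative to each other.

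SAP 7.2.3 plans a liver table (Table 15.11.6.5) with single-test rows and composite rows. The composite closest to Hy's Law is "AST or ALT > 3 x ULN, total bilirubin > 2 x ULN and ALP < 2 x ULN". Others pair AST or ALT >3x ULN with bilirubin >1.5x or >2x ULN and set no ALP condition.

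The two kinds of row are counted differently. Single tests use the worst value on any date: "For individual laboratory tests, subjects will be counted once based on the most severe postbaseline values". For the composites, "subjects will be counted once when the criteria are met at the same postbaseline visit date", and the denominator requires "nonmissing postbaseline values of all relevant tests at the same postbaseline visit date". The section also plans a listing of every subject who meets any one of the criteria (Listing 16.2.8.1.6).

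Under Protocol 6.7.6, liver tests are scheduled on Days 7, 14, 21 and 28 after baseline. "Any test showing an increase of serum AST or ALT" above 3x ULN, or bilirubin above 2x ULN, leads to a repeat of ALT, AST, ALP and bilirubin together after 48 to 72 hours.

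**The concern.** The composite row is the only planned by-arm count of subjects whose transaminase rise came with a bilirubin rise. If bilirubin crosses its threshold after ALT and AST have dropped back, no single date satisfies the criteria and the row records nothing. No other planned summary links a transaminase peak to a bilirubin rise on a later date.

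In a trial of this size one subject decides whether that row reads zero. SAP 2.1 also records that the one scheduled DMC safety review was cancelled, so the end-of-study tables are where a by-arm liver finding would be read.

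**Working it through.** The plan states no figure on this point, so there is nothing to reproduce. The check applies each counting rule to invented subject profiles. Values are multiples of ULN, and AST is taken to be no higher than ALT.

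**Rules compared**

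1. Protocol 3.5, laboratory elements only: ALT or AST >3 on any date, and bilirubin >2 without ALP >2 on any date.
2. SAP 7.2.3, same date: ALT or AST >3 and bilirubin >2 on one date.
3. SAP 7.2.3, same date with ALP: rule 2 plus ALP <2 on that date.
4. Proposed row: ALT or AST >3 at any postbaseline time, and bilirubin >2 on the same or a later date (shown without the ALP condition).

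| Profile | Key dates | Rule 1 | Rule 2 | Rule 3 | Rule 4 |
|---|---|---|---|---|---|
| A: bilirubin later, ALT fallen | Day 7: ALT 4.0, TB 1.2, ALP 1.0; Day 14: ALT 2.5, TB 2.5, ALP 1.1 | yes | no | no | yes |
| B: bilirubin later, ALT still up | Day 7: ALT 6.0, TB 1.2, ALP 1.0; Day 14: ALT 3.5, TB 2.5, ALP 1.1 | yes | yes | yes | yes |
| C: same day | Day 7: ALT 4.0, TB 2.5, ALP 1.0 | yes | yes | yes | yes |
| D: same day, ALP on the boundary | Day 7: ALT 4.0, TB 2.5, ALP 2.0 | yes | yes | no | yes |

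All four subjects also appear in the ALT >3x row, the bilirubin >2x row and the liver listing.

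**What the profiles show**

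- The same-date rule drops a subject only in the pattern of A, where ALT and AST are both at or below 3x ULN on every date with bilirubin >2x ULN. A lag alone is not enough, because B is counted.
- D exposes a separate mismatch. The protocol rules out ALP above 2x ULN, while the SAP requires ALP below 2x ULN, so a value of exactly 2x ULN is classified differently.
- The SAP sentence names the composite of AST or ALT with bilirubin. It does not clearly say whether the row with ALP follows the same-date rule, although the denominator sentence suggests that it does.

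**Effect of the repeat test.** The repeat adds a date on which all four tests are drawn together. It rescues profile A only if bilirubin is already >2x ULN while ALT or AST is still >3x ULN. If the repeat is unchanged or improving, Protocol 6.7.6 returns to weekly monitoring. Whether the repeat enters the composite at all is unclear: SAP 3.8.2 does not assign unscheduled data to a visit, and its post-dose exception for them covers the maximum toxicity grade. SAP 7.2.3, however, takes data from all postbaseline visits.

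**Size.** Protocol 3.3 randomises 60 subjects 2:1, so 60 × 2/3 = 40 on presatovir and 60 × 1/3 = 20 on placebo. One uncounted subject is 1/40 = 2.5% or 1/20 = 5.0%. On presatovir, the row would read 0/40 (exact 95% CI 0 to 8.8%) instead of 1/40 (2.5%, 0.1 to 13.2%).

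**The case against.** The strongest reply is that the two texts do different jobs. Protocol 3.5 is a prompt for the investigator and medical monitor to review a case, with clinical verification. It is silent on timing, which is not the same as saying any time. The protocol's laboratory analysis section (8.7.2) plans no Hy's Law table, and the SAP does not give its row that name. A same-date rule is a legitimate, more specific choice. The tables are descriptive, and every relevant subject is listed. An any-time rule would also join unrelated events: Exclusion 17 bars only ALT or AST above 5x ULN, so a subject may enter at 4x ULN and have an unrelated bilirubin rise weeks later.

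Most of this stands. It makes the point an unreconciled case definition rather than a contradiction, and it shapes the fix. It does not supply the missing by-arm count, and the SAP does not say that the narrowing is deliberate.

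A reader might also infer from the weekly schedule that most lagged cases would fail the same-date test. Assume that ALT falls at once with half-life h days. To exceed 3x ULN after d days it must then start above 3 × 2^(d/h). For h = 2, 3, 5 and 7:

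- d = 7: about 34x, 15x, 8x and 6x
- d = 3: about 8.5x, 6.0x, 4.5x and 4.0x
- d = 2: about 6.0x, 4.8x, 4.0x and 3.7x

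The 7-day figures ignore the repeat at 48 to 72 hours. The half-lives and the immediate decline are assumptions with no source in the documents. They do not support saying that such cases would usually be missed.

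**Conclusion.** The point holds for the composite rows. With the laboratory thresholds fixed, requiring one date can only lower the count, and it lowers it in exactly one pattern: bilirubin >2x ULN only on dates when ALT and AST are both at or below 3x ULN. The effect is one subject at a time, 2.5% or 5.0% of an arm if all 60 randomised subjects enter the Safety Analysis Set. How often this would happen cannot be judged from the documents.

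Three stronger readings are not supported:

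- A reader might infer that a lagged case disappears from the report. It remains in two single-test rows and in the liver listing.
- A reader might infer that the SAP can only undercount relative to the protocol. The protocol's full definition includes clinical verification, which the SAP rows lack, and some SAP composites omit ALP or use a lower bilirubin cut. The SAP can therefore also count subjects whom the protocol definition would exclude.
- A reader might infer that subject management is affected. The SAP rule governs a table only.

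This is a modest gap in a descriptive safety table, worth closing because it is cheap to close.

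**What to change.** In SAP 7.2.3 and Table 15.11.6.5:

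- Keep the same-date rows.
- Add a row for AST or ALT >3x ULN at any postbaseline time through Day 28 with total bilirubin >2x ULN on the same or a later postbaseline date. Show it with and without the ALP condition, and state on which date ALP is read.
- Label the row as laboratory criteria only, without clinical verification.
- Give the row its own denominator, since the existing one requires all tests on one date.
- State that unscheduled repeat tests count in all composite rows, and whether the same-date rule covers the row with ALP.
- Flag subjects whose baseline ALT or AST was already >3x ULN.
- Show test dates in Listing 16.2.8.1.6.

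The ALP boundary must be reconciled between Protocol 3.5 and SAP 7.2.3; this review does not say which is right.

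The ordering (bilirubin on the same or a later date) is deliberately narrower than the protocol's silence on timing. It limits chance pairings, but omits a subject whose bilirubin rises and resolves before the transaminases do.

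The cost is one or two rows in a planned table and no new data. The downside is that a few non-concurrent, non-causal cases may appear and need a narrative.
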